4.7. EFFICACY ANALYSIS

Efficacy summaries for the 52-week treatment period will include outcomes as described in Section 2.6. This includes data from patients collected at unscheduled visits, dosing termination visits, early termination visits, or safety follow-up visits, if the visit date was during the first 52 weeks of the study.

All efficacy endpoints will be plotted in dot plots or box plots.

4.7.1. Covariate Adjustment

Unless otherwise noted, analyses of efficacy endpoints (primary, secondary, and exploratory) will include the following covariates in the model:

- Treatment: placebo, prasinezumab high dose (4500 mg and 3500 mg) and prasinezumab low dose (1500 mg).
- Background therapy at baseline (MAO-B inhibitor treatment): Yes or No.
- Age group: < 60 years vs \geq 60 years.
- Sex: male or female.
- DaT-SPECT contralateral (to the clinically most affected side) putamen binding ratio at baseline.

For each continuous endpoint the baseline of the endpoint will also be included in the model

4.7.2. Primary Efficacy Endpoint

The primary efficacy objective for Part 1 of the study is to evaluate the efficacy of prasinezumab compared with placebo on the basis of total MDS-UPDRS (sum of Parts I, II, and III).

Following the estimand framework outlined in draft the ICH E9 addendum (European Medicines Agency 2017), the attributes of the proposed primary estimand are defined as follows:

- The **population** is defined as the modified intent-to-treat population described in Section 4.1.1.
- The **variable** is absolute change from baseline in total MDS-UPDRS (sum of Parts I, II and III) at week 52 using measurements taken up to the start of symptomatic PD treatment.
- The **intercurrent event** of start of symptomatic PD treatment will be handled with a hypothetical strategy through the MMRM model, i.e. the model will estimate what would have happened to the patients if they had stayed in the trial and not started symptomatic PD treatment. Any other intercurrent event, for example study discontinuation or loss to follow up, that precludes the observation of the primary endpoint will also be handled with the hypothetical strategy.
- The **summary measure** is the difference in absolute change from baseline between each dose level and placebo

MDS-UPDRS

The MDS-UPDRS is a multimodal scale consisting of four subscales (Parts I-IV).

- Part I assesses non-motor experiences of daily living and is comprised of two components:
 - Part IA contains 6 questions focusing on complex behaviors (cognitive impairment, hallucinations and psychosis, depressed mood, anxious

mood, apathy, features of dopamine dysregulation syndrome) and it is assessed by the rater.

- Part IB contains 7 questions on non-motor experiences of daily living (sleep problems, daytime sleepiness, pain and other sensations, urinary problems, constipation problems, light headedness on standing, fatigue) that are part of the Patient Questionnaire completed by the participant.
- Part II assesses motor experiences of daily living. There are 13 questions (speech, saliva and drooling, chewing and swallowing, eating tasks, dressing, hygiene, handwriting, doing hobbies and other activities, turning in bed, tremor, getting out of bed, a car or a deep chair, walking and balance, freezing) that are also part of the Patient Questionnaire completed by the participant.
- Part III assesses the motor signs of PD and is administered by the rater. Part III contains 33 scores based on 18 items (speech, facial expression, rigidity, finger tapping, hand movements, pronation-supination movements of hands, toe tapping, leg agility, arising from chair, gait, freezing of gait, postural stability, posture, global spontaneity of movement (body bradykinesia), postural tremor of the hands, kinetic tremor of the hands, rest tremor amplitude, constancy of rest tremor) several with right, left or other body distribution scores. The rater also marks the patient's clinical state using the following definitions:
 - ON is the typical functional state when patients are receiving approved dopa or dopamine agonist treatment and have good response.
 - OFF is the typical functional state when patients have a poor response in spite of taking approved dopa or dopamine agonist treatment.

Part III subscores are defined as:

- *Bradykinesia*: sum of items 3.4 finger tapping, Items 3.5 hand movements, items 3.6 pronation-supination movements of hands, items 3.7 toe tapping, items 3.8 leg agility, items 3.9 arising from chair, item 3.13 posture and item 3.14 body bradykinesia.
 - *Rigidity*: sum of items 3.3. (Neck, Upper Limbs and Lower Limbs).
 - *Resting tremors*: sum of Items 3.17 rest tremor amplitude (Lip/Jaw, Upper Limbs and Lower Limbs) and Item 3.18 constancy of tremor.
 - *Axial symptoms*: sum of Item 3.10 gait, Item 3.11 freezing of gait and Item 3.12 postural stability.
- In Part IV the rater uses historical and objective information to assess two motor complications, dyskinesias (time spent with dyskinesias, functional impact on dyskinesias) and motor fluctuations (time spent in the OFF state, functional impact of fluctuations, complexity of motor fluctuations, painful OFF-state

dystonia). The Investigator will complete this assessment once a participant has started symptomatic PD treatment.

For each question a numeric score is assigned between 0-4, where 0 = Normal, 1 = Slight, 2 = Mild, 3 = Moderate, 4 = Severe. Composite scores (for each Part and total) are determined by summing the numeric values of each question.

4.7.2.1. Missing Item Values

The number of missing values permissible to render valid scores for each MDS-UPDRS part is defined in accordance with (Goetz et al. 2015), see the table below.

Table 6. Maximal number of allowable missing items for MDS-UPDRS

MDS-UPDRS	Allowable Missing Items
Part I*, IA, or IB	1
Part II	1
Part III	3
Part IV	0

In the case that item 1.6 in Part I is missing, then it will not be considered as missing item towards the total of missing items for Part I. Missing items will not be allowed in Part IA or IB when they are being analysed individually.

Because the MDS-UPDRS has a consistent metric of 0 to 4 ratings across all items, the prorated method is proposed in (Goetz et al. 2015) to calculate a surrogate score for each Part if the number of missing items is below or equal to the maximum threshold defined in Table 6.

If the number of missing items is below or equal to the maximum threshold defined in Table 6, then a prorated score will be calculated as a surrogate score for Part X according to the following formula:

$$\frac{(\sum \text{available scores}) \times (\text{No. total items in the complete part of the MDS UPDRS Part X})}{\text{No. of items with actual scores}}$$

If the number of missing items for a given Part is above the maximum threshold defined in Table 6 then the value for that MDS-UPDRS Part will be set to missing.

If any of the MDS-UPDRS parts is missing, then the MDS-UPDRS Total will be considered missing.

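### The MDS-UPDRS missing-item rules set two limits for Parts IA and IB, and exempt a blank item 1.6 from the missing count but not from proration, so Part I is multiplied by 13/12

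*SAP*

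**What the plan says.** SAP 4.7.2 builds Part I from two blocks: "Part IA contains 6 questions focusing on complex behaviors", the last one listed being "features of dopamine dysregulation syndrome", and "Part IB contains 7 questions on non-motor experiences of daily living". Parts IA, IB and I are each secondary endpoints (SAP 2.3.2), analysed like the primary endpoint (SAP 4.7.3). Part I also enters the primary Total and the time-to-worsening endpoint, where a rise of 3 or more points in Part I is an event.

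The scoring rules are in SAP 4.7.2.1:

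- Table 6 puts Parts I, IA and IB in one row, with one allowable missing item.
- The text below the table says: "Missing items will not be allowed in Part IA or IB when they are being analysed individually".
- If item 1.6 is blank, "then it will not be considered as missing item towards the total of missing items for Part I".
- If the count is at or below the Table 6 limit, "then a prorated score will be calculated as a surrogate score for Part X according to the following formula". The available sum is multiplied by the "No. total items in the complete part of the MDS UPDRS Part X" and divided by the "No. of items with actual scores".
- Above the Table 6 limit, the part is set to missing.

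**The concern.** There are two separate problems.

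First, for Parts IA and IB as endpoints in their own right, the table says one missing item is tolerable and the sentence says none is. The rules that decide between prorating and setting to missing refer to the table alone. Two programmers could follow the section faithfully and produce different Part IA and IB datasets.

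Second, the item 1.6 exemption changes only the count. The formula has no exception, so a blank 1.6 is in effect filled with the patient's mean on items such as sleep, pain and mood. The exemption also names Part I only, so it does not protect Part IA.

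The result is that a score can depend on whether 1.6 was entered as 0 or left blank. If that differs between baseline and a later visit, Part I, the Total and the 3-point event can move without the patient changing, and a Part IA visit can be lost.

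**Working it through.** The plan derives no numerical result from this rule, so there is no figure to reproduce. The check applies the formula as written.

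**Inputs.** Part IA has 6 items and Part IB has 7 (SAP 4.7.2), so Part I has 6 + 7 = 13. Items score 0 to 4. Item 1.6 is taken to be the sixth and last item listed for Part IA; the SAP does not number them. The documents give no Part I level, so S is an assumption and a range is shown.

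**Limit for IA and IB analysed individually.** Table 6: 1. Text: 0.

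**Part I with only 1.6 blank.** Missing items counted = 0, which is within the limit of 1, so the formula applies: S x 13/12 = 1.083 S. Had 1.6 been scored 0, Part I would be S. The excess is S/12.

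| S (other 12 items) | Part I, 1.6 scored 0 | Part I, 1.6 blank | Excess |
|---|---|---|---|
| 6 | 6 | 6.5 | 0.5 |
| 12 | 12 | 13.0 | 1.0 |
| 24 | 24 | 26.0 | 2.0 |
| 36 | 36 | 39.0 | 3.0 |
| 48 (maximum) | 48 | 52.0 | 4.0 |

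**Part I with 1.6 and one other item blank.** The counted missing is 1, still allowed, and the factor is 13/11 = 1.182. Ordinary proration for the other item alone, with 1.6 left out, would be 12/11. For a sum of 12 over the 11 scored items this is 14.18 against 13.09.

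**Part IA with only 1.6 blank.** Under the text: missing. Under Table 6: multiplied by 6/5 = 1.20. This can occur at the same visit as the 13/12 effect on Part I.

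**Three-point Part I event.**

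- *Baseline scored, later visit blank.* With baseline b and a raw rise of 2, the derived change is (b + 2) x 13/12 - b, which reaches 3 when b is 10 or more. At b = 10, the raw sum of 12 becomes 13.0, so a rise of 2 counts as 3.
- *Baseline blank, later visit scored.* A raw rise of exactly 3 becomes 3 - b/12. At b = 4 this is 7 - 4.33 = 2.67, so the event is missed.
- *Blank at both visits.* A raw rise of 2 becomes 2 x 13/12 = 2.17, an overstatement of 0.17. An unchanged patient shows no change.

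**Baseline.** SAP 4.2 takes MDS-UPDRS baseline from the last pre-treatment time point at which Parts I, II and III are all non-missing under these rules. Under the text rule, such a visit can have a valid Part I and a missing Part IA. The section does not say what then serves as the Part IA baseline.

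**The case against.** The sponsor can fairly say that the sentence under Table 6 is a specific exception to a general row: one item may be missing when IA and IB are combined into Part I, and none when either is analysed alone. That is the natural reading. It does not fully settle the matter, because the operative sentences that follow cite only the Table 6 limit.

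Similarly, not counting 1.6 as missing may have been meant to give 12/12. That may be the intention, but the formula does not say so.

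On size, the sponsor has the stronger case. A reader might infer that these rules bias the primary treatment contrast, for which SAP 2.4 plans a 3-point difference. The documents do not support that. S/12 is a shift in one patient at one visit, not a difference between arm means. Part 1 is double-blind, so there is no evident reason for blanks to differ by arm. Protocol 4.6.1.9 asks for a trained specialist rater, with every effort to keep the same rater for each participant, so a consistent habit largely cancels. Missing Part IA visits go to the MMRM.

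A reader might also infer that blanks on 1.6 are common. The special rule suggests that they were foreseen, but no rate is given, and the plan expects every question to receive a score. Nor does proration always inflate: it overstates Part I only if the true 1.6 value is below the patient's mean on the other 12 items, for example 0. If S is 0, or if 1.6 equals that mean, it makes no difference.

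**Conclusion.** The point holds as a minor specification defect. As written, the section gives two limits for IA and IB, and multiplies Part I by 13/12 when only 1.6 is blank (13/11 with one further item blank).

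Against a true 1.6 of 0, a lone blank adds 0.5 points at an assumed S of 6 and 1.0 at 12. The effect on the primary Total is probably small, and more likely noise than a difference between arms. The clearer consequences are Part IA scores that are lost or prorated depending on which rule is followed, and borderline Part I worsening events created or missed. By proration alone, an unchanged patient reaches 3 points only at S of 36 or more.

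The conclusion rests on the literal formula, on 1.6 being the last Part IA item listed, and on assumed Part I sums. The overall effect cannot be sized without the blank rate.

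**What to change.** Amend SAP 4.7.2.1 as follows.

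1. Remove IA and IB from the Table 6 row, so that the no-missing rule in the text governs both when analysed individually, apart from item 1.6.
2. At every visit, leave a blank 1.6 out of both numerator and denominator for Part I: 12/12 if only 1.6 is blank, 12/11 if one other item is also missing. For Part IA, do not treat a blank 1.6 as missing; use the sum of the other five items.

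The rule should apply regardless of dopaminergic treatment. Visits after treatment starts are used in the time-to-worsening analysis (SAP 4.7.3) and the OFF-state sensitivity analysis (SAP 4.7.4). A rule confined to untreated visits would leave those blanks without a rule, or let the score change with treatment status.

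In the worked example, the later Part I becomes 12 x 12/12 = 12, the rise is 2, and no event is recorded. When another item is also missing, blank and zero still differ slightly, by S x (12/11 - 13/12) = S/132, or 0.09 points at a sum of 12 over the 11 scored items.

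The cost is a few lines of text and a change to the score derivation, with no new data. The downside is that a blank 1.6 contributes nothing, so a true non-zero value would be missed. The fix assumes that 1.6 is usually 0 in participants not on dopaminergic drugs, which the documents do not establish.

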4.7.2.2. Primary Analysis

The primary efficacy endpoint will be analyzed using a Mixed Model for Repeated Measures (MMRM) using the covariates described in Section 4.7.1 as fixed effects. The

model will also include week of treatment (as a categorical factor) and a treatment-by-visit interaction term, an interaction term between baseline MDS-UPDRS by visit will also be included. Within each participant, the model will incorporate an unstructured variance-covariance matrix for the random error terms. If the unstructured covariance matrix is non-estimable other covariance structures like heterogeneous autoregressive or compound symmetry would be used. Parameters will be estimated with the use of restricted maximum likelihood, and the Kenward-Roger method will be used for calculating the denominator degrees of freedom. Observations from different participants are considered independent. This model will be used to test the null hypothesis of no treatment difference at a two-sided α -level of 20% for the following comparisons:

- High dose vs placebo,
- Low dose vs placebo.

All the assessments that started after the “first symptomatic PD treatment date” (as defined in Section 4.3.1) will not be included in the analysis.

Missing scores (due to the assessments performed after the starting of symptomatic PD treatment or any other reason) for each of the individual parts of the MDS-UPDRS will not be imputed; they will be handled via the MMRM model. The MMRM assumes that missing data are missing at random (MAR). That is, MMRM assumes that given the statistical model and given the observed values of the endpoint, missing data are independent of the unobserved values (O’Kelly and Ratitch 2014). Correlation between successive observations on a subject allows data from subjects who dropped out to make a contribution to estimation of the effects at the final time point. The primary endpoint will also be summarized using descriptive statistics.

A cumulative distribution plot will be presented to show the proportion of responders when each possible cutoff point of the MDS-UPDRS total score (sum of Parts I, II, and III) is used as the definition of response. The proportion of patients in each treatment group with each unit of improvement or worsening will be presented in a cumulative plot. At a particular change from baseline MDS-UPDRS score x , the proportion of patients with a change of baseline value $\geq x$ will be presented in the cumulative plot. All the assessments flagged on and after the “first symptomatic PD treatment date” (as defined in Section 4.3.1) will not be included in the analysis.

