2.4. DETERMINATION OF SAMPLE SIZE

The sample size calculations were aimed to power the study for the primary endpoint of change in total MDS-UPDRS (sum of Parts I, II and III) at Week 52, see Section 4.7.2 for a full description of the endpoint.

A sample size of 100 randomized participants per group (300 participants for the three groups) was chosen to obtain a power of approximately 80% at two-sided α -level of 20% for the comparison of each active dose arm to placebo. The power calculation was based on simulations of the mixed-effect model repeated measures (MMRM) analysis

planned for the primary efficacy variable. Assessments performed while on any symptomatic treatment started after randomization will not be included in the analysis. The following assumptions were made for simulating the data:

- Seven post-baseline assessment visits,
- An overall rate of missing values (due to participants starting symptomatic therapy or prematurely withdrawing from study medication during the 52-week placebo-controlled treatment period) of 25% in the placebo group and 20% in each dose group at Week 52, with incremental rates over the 52-week placebo-controlled period
- A linear mean increase of the primary endpoint (natural progression) of eight points/year for the placebo arm, with a linearly increasing common standard deviation reaching nine points at Week 52
- An effect size of 0.33 (difference=3 points, relative reduction of progression=37.5%) for one dose group versus placebo at Week 52 with increasing magnitude of treatment difference over the placebo-controlled period
- A compound symmetry correlation structure assuming a correlation coefficient of 0.55 between different visits.

Table 1 provides the additional information needed to perform the simulations.

Table 1. Assumptions Used for Simulations

Post-Baseline Visit (weeks)	8	16	24	32	40	48	52
Change from baseline in MDS-UPDRS total (sum of Parts I, II, and III), placebo arm (points)	1.2	2.4	4	4.8	6	7.2	8
Change from baseline in MDS-UPDRS total (sum of Parts I, II, and III), active treatment arm (points)	0.8	1.5	2.5	3.0	3.8	4.5	5
Common standard deviation for change from baseline in MDS UPDRS total (points)	6.75	7.25	7.75	8	8.5	8.75	9
Percentage of patients with non-evaluable data, placebo*	1%	3%	5%	7%	17%	22%	25%
Percentage of patients with non-evaluable data, treatment*	1%	3%	5%	7%	12%	17%	20%

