Symbol Digit Modalities Functional Test	Total Score
Passive Monitoring – Turning	Median Turn Speed
Passive Monitoring – Gestures	Median Turn Speed

Each feature will be first normalised. Feature values will be aggregated by average over reported window (Table 5). Feature values will be considered missing if less than 3 feature values exist in this interval. The same random coefficients model used for primary analysis will be used for analysis of the dBm features. Assessment taken after the start of symptomatic PD treatment (described in Section 4.3.1) will not be included in the analysis.

Absolute change in digital PASADENA motor score – Remote Monitoring

The digital PASADENA motor score will be mapped according to the time windows described in Table 5. An average of the dBm score will be calculated for each visit using all the scores that are mapped within a single reporting window. Assessment taken after the start of symptomatic PD treatment (as described in Sections 4.3.1) will not be included in the analysis. A random coefficients model will be used for the analysis of the

dBM. The model involves a random intercept and a slope for each subject. Within each participant, the model will incorporate an unstructured variance-covariance matrix for the random error terms. If the unstructured covariance matrix is non-estimable other covariance structures like heterogeneous compound symmetry would be used. Parameters will be estimated with the use of restricted maximum likelihood, and the Kenward-Roger method will be used for calculating the denominator degrees of freedom.

Percent change in digital PASADENA motor score - Remote Monitoring

Percent change in digital PASADENA motor score will be analyzed in the same way as the absolute change in digital PASADENA motor as described above

Digital PASADENA motor Score – In Clinic Assessments

The digital PASADENA motor score derived from in clinic assessments will be analysed as the one obtained from remote monitoring, the only difference will be that the average of the dBM score will be over the time windows described in Table 4

Digital Biomarker Single Features – In Clinic Assessments

Selected features from the digital biomarker in clinic assessments will be analysed in the same way as the features from the remote monitoring.

dBM ePROs: PAC-SYM, Hospital Anxiety and Depression Scale (HADS), EQ-5D-5L will be analysed via ANCOVA and/or random coefficients model.

Diary Questions

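### If the unstructured fit fails, the unordered fallback list for the primary MMRM admits plain compound symmetry, which could raise the Week 52 test from 20% to as much as about 26% two-sided

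*SAP*

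**What the plan says.** For the primary endpoint, SAP 4.7.2.2 states that "the model will incorporate an unstructured variance-covariance matrix for the random error terms". The contingency follows at once: if that matrix cannot be estimated, "other covariance structures like heterogeneous autoregressive or compound symmetry would be used". Estimation is by REML, and "the Kenward-Roger method will be used for calculating the denominator degrees of freedom"; no robust (sandwich) variance is named. Each dose is tested against placebo at a two-sided 20% level. Protocol 6.6.1 also plans an unstructured matrix and names no fallback.

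The power simulations in SAP 2.4 assume a constant correlation of 0.55 between visits, together "with a linearly increasing common standard deviation reaching nine points at Week 52". Table 1 there (identical to Protocol Table 4) gives the SDs by visit.

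In SAP Appendix 1, the corresponding sentence for the digital motor score reads "other covariance structures like heterogeneous compound symmetry would be used".

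The primary model is used again elsewhere. SAP 4.7.3 applies it to the MDS-UPDRS sub-scores, and SAP 4.7.5 fits it within every subgroup that holds at least 20% of the mITT population.

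**The concern.** There are two defects in the one sentence.

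1. The alternatives are given as examples, with no order and no selection rule. The covariance structure behind the primary test is therefore not fixed in advance once the first choice fails. This holds however compound symmetry is read.
2. Compound symmetry without a qualifier means one variance common to all visits. The plan's own assumptions say otherwise, and Week 52, the visit being tested, has the largest SD. Pooling it with the smaller SDs of earlier visits makes the Week 52 standard error too small. Kenward-Roger adjusts for estimating the covariance parameters; it does not repair a structure that is wrong.

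At stake, should that branch be taken, are the stated 20% level and the coverage of the 80% intervals. No multiplicity adjustment stands behind the two dose comparisons to absorb the excess.

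**Working it through.** **Inputs** (SAP 2.4 and Table 1): 100 patients per arm; visits at Weeks 8, 16, 24, 32, 40, 48, 52; SDs 6.75, 7.25, 7.75, 8, 8.5, 8.75, 9; correlation 0.55; difference 3 points at Week 52; cumulative missingness 1, 3, 5, 7, 17, 22, 25% on placebo and 1, 3, 5, 7, 12, 17, 20% on active, taken as monotone. The two-sided level is 20%, so z = 1.2816. A mean is fitted for each arm and visit; covariates are left out.

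**Step 1. Reproduce the plan's power.** With the true covariance, the generalised least squares standard error of the Week 52 difference is 1.374. Power = Φ(3/1.374 − 1.2816) = Φ(0.90) = 81.6%, against the plan's figure of about 80%. Simple brackets agree:
- Completers only: SE = 9·√(1/75 + 1/80) = 1.446, power 78.6%.
- No missing data: SE = 9·√(2/100) = 1.273, power 85.9%.

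**Step 2. A rough check without missing data.** Plain compound symmetry estimates one variance, in the limit the mean of the squared SDs: 452/7 = 64.57, so the pooled SD is 8.04. The ratio to the true Week 52 SD is 8.04/9 = 0.893. Size = 2·(1 − Φ(1.2816 × 0.893)) = 25.3%.

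**Step 3. With the planned missingness.** For a working matrix W and true matrix S, each arm contributes A = Σ W⁻¹ and B = Σ W⁻¹SW⁻¹ over the observed patterns. The model variance is A⁻¹ and the true variance is A⁻¹BA⁻¹. The contrast sums the Week 52 diagonal entries of the two arms. W is the likelihood limit of each structure. Actual size = 2·(1 − Φ(1.2816 × model SE / true SE)).

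| Structure fitted | Model SE | True SE | Two-sided size | Power |
|---|---|---|---|---|
| True covariance | 1.374 | 1.374 | 20.0% | 81.6% |
| Heterogeneous compound symmetry | 1.374 | 1.374 | 20.0% | 81.6% |
| Heterogeneous autoregressive | 1.433 | 1.418 | 19.5% | 79.4% |
| Plain compound symmetry (SD 7.95, correlation 0.54) | 1.216 | 1.377 | 25.8% | not comparable (level inflated) |

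For plain compound symmetry the ratio is 1.216/1.377 = 0.883, and 1.2816 × 0.883 = 1.132, which gives 25.8%. A nominal 80% interval then covers 100 − 25.8 = 74.2%. Giving every arm the placebo missingness yields 25.9%.

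**Step 4. Simulation under the null.** REML fits of plain compound symmetry in 3,000 trials gave 26.1% with the planned missingness and 24.3% with complete data. The Monte Carlo error is about 0.8 points per comparison.

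**Step 5. Sensitivity to the SD profile.** Table 1 gives SDs of raw change, but the model uses residual SDs after baseline, baseline-by-visit and the other covariates. The documents do not give these. Holding Week 52 at 9 and shrinking each earlier shortfall, SD = 9 − f·(9 − Table 1 SD):

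| f | Two-sided size |
|---|---|
| 1 | 25.8% |
| 0.75 | 24.3% |
| 0.5 | 22.8% |
| 0.25 | 21.4% |

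**Step 6. How likely is the branch?** An unstructured 7 × 7 matrix has 7·8/2 = 28 parameters. With about 300 patients, failure is unlikely. A subgroup at the 20% threshold has about 0.20 × 300 = 60 patients, or 20 per arm, and needs the same 28 parameters, so failure is more plausible there. The SE ratio in Step 3 does not depend on n in this large-sample calculation, so subgroup intervals would be too narrow in about the same proportion if residual SDs rise similarly.

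**The case against.** The strongest reply is that the inflation needs three things at once: the unstructured fit fails, compound symmetry is picked over the other named structure (which holds the level at about 19.5%), and compound symmetry means the homogeneous form. All of that stands. A reader might infer that the Week 52 test will run at 26%. The documents do not support that, because the planned analysis is unstructured and its level is untouched.

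The third condition is open. The adjective in SAP 4.7.2.2 can govern both terms. SAP 2.4 uses the unqualified term for a correlation pattern combined with rising SDs, which is heterogeneous compound symmetry in substance. Appendix 1 can be read either way. Spelling out the heterogeneous form there may signal a deliberate contrast, or it may show a shared intent loosely worded in 4.7.2.2. The literal reading is the homogeneous one, but the text does not prove the sponsor meant it. Clarification is needed on either reading.

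A reader might also infer that the structure would be chosen after seeing results. Nothing in the documents suggests such an intention; they only fail to rule it out.

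Finally, Table 1 holds raw SDs, so a single figure of 26% claims too much. That stands, and Step 5 gives the range.

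**Conclusion.** The point holds as a conditional one. The fallback sentence is unordered and, read literally, admits a structure that contradicts the plan's own variance assumptions. If plain compound symmetry were used, the two-sided size at Week 52 would be about 26% if residual SDs rise as steeply as Table 1, and about 21% to 24% if they rise a quarter to three-quarters as steeply. These figures rest on the Table 1 SDs and missingness, a constant correlation of 0.55, monotone dropout and 100 patients per arm.

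The documents give no probability that the unstructured fit fails. For the primary analysis it is unlikely; for the smallest subgroups of SAP 4.7.5 it is more plausible. The finding does not challenge the primary analysis as planned. It is a cheap improvement to a contingency rule, which should preserve the stated level when it is called on.

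**What to change.** Replace the fallback sentence in SAP 4.7.2.2 with a fixed order limited to structures with visit-specific variances, and take the first that converges:

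1. Heterogeneous compound symmetry. It matches the constant 0.55 correlation with rising SDs in SAP 2.4 and keeps the level at 20.0%.
2. Heterogeneous first-order autoregressive. It comes second because an index-based version treats the 4-week gap from Week 48 to Week 52 like the 8-week gaps before it, and because under the plan's assumptions it has slightly less power (79.4% against 81.6%).

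Delete plain compound symmetry, or allow it only as a last resort with a sandwich variance, stating the degrees of freedom to go with it. Say that the same order applies to the sub-scores in 4.7.3 and the subgroups in 4.7.5.

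The cost is one or two sentences and slightly less flexibility. Nothing changes when the unstructured model converges, and neither the sample size nor data collection is affected.
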